4.2 Patient Identification

Patients will not directly receive intervention, but their clinical parameters will be used to identify upcoming visits with potential opportunities for prescription of an SGLT-2i or GLP-1RA medication. As with prior work, we will use the hospital's EHR database, the Epic Enterprise Data Warehouse, to identify eligible patients.

4.3 Recruitment Procedures

We will use the hospital's EHR database, the Epic Enterprise Data Warehouse, to identify eligible patients.

As with similar minimal-risk quality-improvement studies that we have performed that involve the use of routine clinical tools such as patient portals or physician reminders, informed consent will not be sought in this study, and we request a waiver of informed consent. The nature of this intervention involves the use of messages delivered via email and in-basket (using information already available to providers and delivered via a similar infrastructure they use during regular clinical care). Obtaining written informed consent would also not produce generalizable knowledge about the effectiveness of the intervention, a foundational aspect of pragmatic clinical trial principles. With an approved waiver of informed consent for provider participation, all attending MGH primary care providers will be directly included in the study.

While providers and patients will not be consented into the study, an organization-wide announcement will be circulated across MGH Primary Care Practices to inform providers of the launch of this support for improved prescribing for adults with sub-optimally controlled diabetes.

Providers will be able to request unenrollment from the study at any time by replying to the intervention email. However, because the intervention includes only emails and in-basket messages that support prescribing, we anticipate that retention rates in the study will be very high. Study staff and data analysts will track any physician turnover in the study as they have done in prior work, and though minimal physician turnover is expected, we expect any turnover to bias the trial results towards the null.

5. Subject Enrollment

We will use the hospital's EHR database, the Epic Enterprise Data Warehouse, to identify eligible patients.

5.1 Informed Consent

As with other minimal-risk studies we have performed where informed consent is impracticable, we are requesting a waiver of informed consent and HIPAA authorization for patients and providers. There are several reasons for this. First, we plan to use routinely collected EHR data to identify eligible providers, administer interventions, and assess study outcomes. Because this is of minimal risk to patients, the study team will have no interaction with patients, all medical decisions will be made by the patients' PCP as in usual care, and it would be impracticable to obtain patient consent, we feel that a waiver of consent and HIPAA authorization for patients is needed for this study. Similarly, for providers, the interventions are minimal risk, designed to provide decision support for diabetes care, are consistent with professional guidelines and MGH-specific quality metrics, and are similar to supports that are put in place in routine quality improvement interventions. The interventions will be delivered using email and Epic in-basket which are routinely used in primary care. Providers will be given the opportunity to unenroll from the study at any time by replying to a study email or by contacting the study team; if they request to be unenrolled they will receive no further study-related contact.

5.2 Treatment assignment and randomization

All eligible providers will be randomized in a 1:1:1 ratio to one of three arms: (1) intervention to address diffusion of responsibility, (2) intervention to address diffusion of responsibility plus additional simplification of the prescribing process, and (3) usual care. Randomization will be stratified by primary care clinic.

6. STUDY PROCEDURES

6.1 Study Site

Study participants will be selected from Mass General Brigham (MGB), a large integrated delivery network in Boston, MA, specifically from Mass General Hospital primary care clinics, where [name] (PI) practices.

6.2.1 Aim 1 Design

In Aim 1 of the study, we will conduct a 3-arm randomized controlled trial to compare the effectiveness of two interventions compared to usual care on SGLT-2i and GLP-1RA prescribing. We will include Massachusetts General Hospital Attending Primary Care Providers. Interventions will be linked to upcoming visits with patient aged 18-84 years with poorly controlled type 2 diabetes (HbA1c >7.0%) and a compelling indication for an SGLT-2i or GLP-1RA (including cardiovascular disease, kidney disease, heart failure, or obesity), who are not already prescribed one of these therapies. We will exclude patients with a documented allergy to both medication classes, end stage renal disease, dementia, type I diabetes, an EHR indicator of hospice care and those who are excluded from the MGH diabetes registry.

Providers will be randomized equally to one of three arms: (1) intervention to address diffusion of responsibility, (2) intervention to address diffusion of responsibility plus additional simplification of the prescribing process, and (3) usual care. The intervention period will continue for 6 months.

Providers randomized to arm 1, an intervention to address diffusion of responsibility, will receive an email from a peer offering encouragement and support in prescribing SGLT-2is and GLP-1RAs that includes specific components designed to reduce diffusion of responsibility. Specifically, these elements are adapted from interventions that mitigate diffusion of responsibility in other contexts, including (1) assigning a responsibility to individuals or smaller groups, (2) increased perceived harm of the situation to be addressed (3) highlighting competence to act, and (4) modeling the desired behavior. The email will also contain an offer for direct support from the peer. Four MGH primary care physicians will administer the intervention. The email will be sent by the study team on their behalf and will contain a personalized subject line and/or text to increase the likelihood of opening and reading (see Study Interventions Document]).

The email will be accompanied by an additional personal outreach like walking through the practice and initiating brief, informal conversation or a short, hand-written note left on the PCP's desk 3-4 and 6 months after the start of the intervention. After the initial email, PCPs will receive up to 3 additional follow-up Epic in-basket messages, per provider, per week, notifying them of patients with upcoming visits who are eligible for one of these therapies and offering support in prescribing. The PCPs delivering the intervention will be trained in the clinical and administrative nuances of prescribing SGLT-2is and GLP-1RAs and remunerated for time spent assisting their peers. They will also have access to a diabetologist to consult for challenging clinical questions. Any additional interactions between study PCPs and the peer delivering the intervention will be offered and tracked but not required. If providers assigned to this arm reach out with questions about prescribing, the peer will respond and may provide clinically existing resources that are currently available in routine care.

Providers randomized to arm 2, an intervention to address diffusion of responsibility plus additional simplification of the prescribing process, will receive the same contact addressing diffusion of responsibility as in arm 1, but they will additionally have access to an experienced administrative team for diabetes medication insurance authorization support. In this arm, the list of each PCP's patients who are potentially eligible for an SLGT-2i or GLP-1RA will be reviewed by MGH's Central Authorization Unit (CAU). The CAU is an administrative team that currently supports prescribing for MGH diabetes specialists and other divisions by completing insurance authorization requests and helping providers

navigate variable insurance coverage for medications. For eligible study patients, the CAU will review the patient's chart and insurance coverage and provide information on which medication options are likely to be most affordable for each patient. This information will then be sent to PCPs via Epic in-basket message 3 business days before the patient's visit. In-basket messages will come from the shared inbasket pool, be signed by both the PCP peer and the CAU team, and will contain information about which SGLT-2is and GLP-1RAs are covered for that patient. In-basket messages will be capped at no more than 3 per provider per week, providers will be messaged about a single patient no more than 3 times over the course of the study. PCPs will also be informed in the initial outreach how to access the administrative team through Epic in-basket or email with any administrative questions or for any followup.

As in Arm 1, the initial email will be accompanied the additional personal outreach 3-4 and 6 months after the start of the intervention, and up to 3 follow-up Epic in-basket messages per provider, per week, but in Arm 2 the follow-up messages will also include information on the covered medication choice(s) for each patient how to access additional CAU support. Providers will be invited to reply directly that in-basket message to request assistance with prior authorization if needed. This team will then follow up with the pharmacy to determine coverage, communicate with clinic medical assistants, complete prior authorizations, determine alternative covered options, and track the process, as needed in each case. From the primary care doctor's perspective, this will be a markedly smoother process than current prescribing. If providers assigned to this arm reach out with questions regarding insurance coverage or prior authorization for an eligible patient that does not have an upcoming visit, the CAU staff will deliver the intervention with covered medication choice(s) to the provider at that time. If the patient later has an upcoming visit and has still not been prescribed the medication, the CAU staff will deliver the intervention again in the typical time frame (3 business days prior to the visit). Interventions regarding a single patient will be capped at no more than 3, including any interventions not associated with visits but delivered after PCP request. If providers assigned to this arm reach out with questions regarding ineligible patients, PCP peers will provide them with the same generic resources given in arm 1 that are currently available in routine care.

Prior to enrollment of providers into this trial, the CAU will pilot test Epic in-basket versus email workflow to determine the most efficient workflow. This pilot testing will be done with panels of those PCPs who are not included in the study due involvement in the study (i.e., PI and peer providers).

All providers will receive the second personal outreach 6 months after the start of the intervention. The outreach will consist of an email notifying them that the study is ending and inviting them to participate in a brief survey. The fact sheet for survey participation will be attached to the email. The survey will be accessed through a unique link to a secure REDCap survey embedded into the email. REDCap is a secure, HIPAA-compliant web-based platform hosted on Mass General Brigham servers. Providers who click on the link to the survey will be met with a landing page that displays the fact sheet describing the study. They will then be able to click a button to indicate that they agree to participate. Providers who select that they agree will then proceed to the rest of the survey. All providers will be allows to respond. Participants will be offered remuneration in the form of a \$25.00 Amazon gift card for completing the survey. An email will be sent to the physician upon completion of the survey containing the claim code they will use to access their gift card. In addition, an electronic copy of the prescribing chart given to intervention arms, providers will also receive a list of the patients who remain eligible for one of these medications but who have not had a visit during the study intervention period. Providers will then have

the option to ask their administrative staff to schedule visits with these patients, consider prescribing asynchronously, or otherwise generate a plan of care. The survey to intervention providers will capture opinions on the interventions, mechanisms behind diffusion of responsibility in prescribing these medications, and thoughts about potential helpful interventions moving forward. Providers in the control arm will only be asked the questions about mechanisms behind diffusion of responsibility in prescribing these medications and thoughts about potential helpful interventions moving forward. All providers who have not completed the survey within 2-3 weeks of receiving the email invitation will receive a follow-up email asking them again to participate in the survey.

Providers randomized to arm 3, usual care, will not receive any outreach outside of the end of study notification and survey.

After study completion, we will conduct an exploratory chart review of the visit notes from a random sample of patients in all three arms. Within each study arm, we will randomly sample visit notes from charts of 20 patients who were prescribed an SGLT-2i or a GLP1RA during the target visit (primary outcome occurred) and 20 patients who did not receive a prescription (primary outcome did not occur) to qualitatively explore the nature of the conversations that were documented at the visit. This will also include reviewing other encounter types in patients charts like telephone notes, patient gateway messaging, and other visits. This data collection will come from Epic chart review only. We will review the chart and summarize the nature of that conversation that was had around initiating SGLT-2is or GLP-1s, if one was documented. We will review the notes from the visit that was targeted by the intervention as well as subsequent notes in the chart as needed (such as telephone encounters, patient gateway encounters, and specialists visits notes) in order to understand if a medication was prescribed, and if not, then what the barriers were to starting. We will collect information on whether the patient filled the new prescription at the pharmacy, if available. This will include a total of 120 sampled charts, and the qualitative analyses will help us identify potential characteristics to extract from routine EHR data for Aim 2 and help understand remaining barriers to prescribing as well as potential mechanisms behind intervention effectiveness. Finally, we will also review the charts of all patients who received a prescription for a new medication to see what proportion of these prescriptions were actually filled by patients.

We will use the MGB standardized deployments of AI/ML services in MGB's secure cloud infrastructure, specifically the Azure OpenAI models as a tool to analyze qualitative data from the study and compare results from the LLM to those obtained by investigator analyses. Use of the LLM will permit faster analysis of large amounts of qualitative free-text data.

6.2.2 Aim 2 Design

In Aim 2, we will identify characteristics of providers, patients, and their interactions, that are measurable in routinely collected EHR data, that are associated with intervention responsiveness. We will extract provider demographic and practice data, patient demographic and clinical information, and data on the patient-provider interaction. We will also pre-specify which of these characteristics may be related to diffusion of responsibility.

6.3 Participant Remuneration

Subjects will be remunerated for participation in the end-of-study survey. Providers who complete the survey will receive a \$25 Amazon gift card; an access code for their payment will be delivered by email.

7. Risks and Discomforts

We believe there is no more than minimal risk involved to the physician subjects, as the physicians will receive interventions designed to help with the provision of guideline-concordant diabetes care. The study recommendations are consistent with professional guidelines and MGH-specific quality metrics and are similar to supports that are put in place in routine quality improvement interventions. The interventions will be delivered using email and epic in-basket which are routinely used in primary care. The main potential discomfort for providers is burden from receiving additional messages. To mitigate this, messages will be kept to the minimum necessary to deliver the intervention, and providers will be given the opportunity to unenroll from the study at any time by replying to a study email or in-basket message. If they request to be unenrolled, they will receive no further study-related contact.

For patient-subjects, we also believe that the risks, to participation is no more than minimal for several reasons. First, the interventions aim to emphasize guideline-recommended treatments for patients with diabetes and a compelling indication for these treatments. Second, all treatment decisions will ultimately be made by licensed primary care physicians. Finally, the intervention is specifically physician-focused and uses information already available to physicians. There is a small risk associated with altering diabetes medication prescribing, including hypoglycemia, allergic reactions, and others. However, the diabetes control and cardiovascular benefits of these medications are typically considered to outweigh the infrequent risks, and PCPs can weigh these risks and benefits with each individual patient and decide whether or not to prescribe, as they always do in usual care. For this reason, we believe the potential risks of treatment initiation as part of this trial are the same as what is encountered during routine, guideline-concordant diabetes care. The study team will not be providing any direct care to patients and all medical decisions are ultimately made by the physician. This trial will otherwise not interfere with the usual workings of primary care practices. Thus, the main potential risk to subjects in this study is related to privacy of data, and we will take several measures to ensure that this risk is minimal, and that patient information is safeguarded.

Patient data for study outcome evaluation will be drawn from EHR information in the Epic Enterprise Data Warehouse (EDW). The investigators are aware of the sensitive nature of the data and are committed to protecting patient privacy. Only the minimum necessary identifiable health care data needed to achieve the intended purpose will be used. All the data in the registry is contained within the Mass General Brigham firewall, and its usage is logged and audited. It is only accessible to IRB-approved researchers. In addition, supplementary qualitative data for implementation evaluation will be drawn through traditional chart review by the research assistants. Research assistants will review conversations documented through multiple encounter types, like telephone notes, patient gateway messaging, and other visits and summarize what happened. Information will only be summarized from encounters that are viewable from the patient's chart; we do not need access to provider-to-provider inbasket messaging that is not saved into the chart. Summarized qualitative information will be stored using a secure REDCap database and all efforts will be taken to ensure that this information is safeguarded and only accessible to study investigators who are actively involved in the research.

For all study data, we will safeguard any identifiable information in accordance with IRB practices, limit access to the information to study investigators actively involved in the research who have all undergone human subjects research training and store any data in accordance with IRB practices. Finally, as is our routine practice, great care will be taken to ensure the confidentiality of all data and to protect the privacy of participants through translation of all potentially traceable identifiers into untraceable coded subject numbers whenever possible. To ensure the confidentiality and security of all data, the research team operates a secure, state-of-theart computing facility housed at MGB's data center. The MGB data center is a secure facility that houses both computing environments as well as clinical systems and electronic medical records for several large hospitals in Eastern Massachusetts. Entry into the computer room requires staffed computer room security. The Division's computers are connected to the MGB networking backbone with 10 gigabit-persecond fiber links. Network security is overseen by electronic medical records systems to the research team's data. All data are transmitted to programmers' workstations in an encrypted state. Backups are created using 256-bit AES encryption, the current Department of Defense standard for data security, and are stored in a locked facility. The redundancy, extensive data power, and security of our computer facility confirm our capacity to collect and manage data and ensure confidentiality for all project participants.

For the use of the Azure Open AI models, we will utilize the secure MGB environment on the Azure cloud to access the Open AI tools. The cloud setup has been previously established by MGB for research team use and complies with the legal, cybersecurity, and data security requirements at MGB. Our team has completed a Cloud Architecture Consult with the IT team and we will abide by MGB's published AI/LLM Guidance. Within the Azure environment, only team members included on the IRB who are participating in the data analysis will be given access to the LLM and data, following the same principles for our data management in other systems.

8. Benefits

Interventions to address diffusion of responsibility and simplify the prescribing process could help increase utilization of SGLT-2is and GLP-1RAs in diabetes care. Thus, the research could have both immediate benefits for physicians by increasing diabetes treatment knowledge, as well as for their patients who might benefit from improved glycemic control.

9. Statistical Analysis

9.1 Data Analysis Plan

9.1.1 Aim 1 Analysis Plan

For analyses we will use generalized estimating equations to compare outcomes between each intervention versus usual care and each other.

Qualitative analyses will be conducted on the random sampling of charts from patients who did and did not have the primary outcome in each study arm. Data will be coded and themes extracted and used to inform interpretation of the primary and secondary outcome results.

We will use the Azure Open AI LLM to assist with data analysis of free text qualitative data including that from chart review and free-text responses from physicians to the survey. Specifically, we will engineer prompts to guide the LLM in coding of data, extraction of themes, and summary of content. This will be used to compliment direct qualitative analysis by study investigators and will permit faster analysis of qualitative data. Results from this will be reported as part of trial results and will also help inform which predictors may be impactful for Aim 2.

9.1.2 Aim 2 Analysis Plan

For analyses, we will fit separate logistic and boosted regression models using sets of these predictors to evaluate the ability to predict responsiveness to each intervention, and we will incorporate classification

and regression trees where appropriate. Boosted regression is a machine learning method robust to multi-collinearity and overfitting. For each regression, we will use 10-fold cross-validation to compare C-statistics for the ability to predict intervention response and calculate a continuous net reclassification index to assess changes in predicted response with additional predictors.^{26,27}

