Aim 1: Test the impact of an intervention to target diffusion of responsibility with and without additional reduction in prescribing burden on SGLT-2i and GLP-1RAs prescribing compared to usual care. We will conduct a randomized trial among primary care providers. The primary outcome will be SGLT-2i and GLP-1RA prescribing for patients with poorly controlled type 2 diabetes and a clear indication for one of these medications.

[figure not shown]
Aim 2: Identify characteristics of the patient, provider, and their clinical interaction that are associated with responsiveness to each intervention using routinely collected EHR data. The effectiveness of these interventions may vary based on characteristics of patients, providers, or the clinical scenario. Identification of predictors of responsiveness will help target interventions to those most likely to benefit.

3. General Description of Study Design

This study will be conducted within MGH primary care. As with prior work, we will use the hospital's EHR database, the Epic Enterprise Data Warehouse, to identify patients. Patients will be eligible if they are: adults 18-84 years of age with poorly controlled type 2 diabetes (defined as HbA1c >7.0%) and a compelling indication for an SGLT-2i or GLP-1RA (including cardiovascular disease, kidney disease, heart failure, or obesity), who are not already prescribed one of these therapies. We will exclude individuals with end stage renal disease, dementia, type I diabetes, or an EHR indicator of hospice care. We will also exclude patients who are not on the MGH diabetes registry, because patients who are excluded from the registry typically have a clinical reason for alternative diabetes goals or care plans. All attending MGH PCPs (excluding those involved in the design or delivery of the intervention) will be included in the trial. Eligible PCPs will be randomized to one of three arms: (1) intervention to address diffusion of responsibility, (2) intervention to address diffusion of responsibility plus additional simplification of the prescribing process, and (3) usual care. Providers randomized to arm 1, the intervention to address diffusion of responsibility will receive an email from a peer offering encouragement and support in

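### Aim 2 does not allow for patients sharing a PCP, so provider characteristics could look more predictive of response than they are

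*Combined protocol and SAP*

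**What the plan says.** Section 5.2 makes the PCP the unit of randomisation: "All eligible providers will be randomized in a 1:1:1 ratio to one of three arms". Section 9.2 assumes an ICC of 0.07 and an average of 7 patients per provider, so the plan itself expects outcomes to be correlated within a PCP.

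Aim 2 in section 2 is to "Identify characteristics of the patient, provider, and their clinical interaction that are associated with responsiveness to each intervention". Section 6.2.2 repeats the goal as finding characteristics "that are associated with intervention responsiveness" and includes provider-level variables among the predictors: "We will extract provider demographic and practice data, patient demographic and clinical information, and data on the patient-provider interaction".

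The method in section 9.1.2 is "we will fit separate logistic and boosted regression models using sets of these predictors", with classification and regression trees where appropriate. For the outputs, "we will use 10-fold cross-validation to compare C-statistics for the ability to predict intervention response", and the team will "calculate a continuous net reclassification index to assess changes in predicted response with additional predictors". The section names no GEE, robust variance, random effect or other cluster step. It does not say whether folds are formed by patient or by PCP.

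By contrast, section 9.1.1 says of Aim 1 that "we will use generalized estimating equations to compare outcomes between each intervention versus usual care and each other". It does not name the cluster unit.

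**The concern.** A characteristic of the PCP takes one value for all of that PCP's patients. The information about it therefore comes from the number of PCPs much more than from the number of patients. An ordinary logistic model counts each patient as independent and so overstates that information. GEE appears in one subsection and logistic regression in the next, so an analyst following the text would naturally fit an ordinary logistic model to Aim 2.

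The same omission reaches the prediction measures. If some of a PCP's patients are in the training folds and others in the test fold, a model can use provider variables to recognise the PCP and carry over that PCP's own prescribing level. Predictors with no general value then appear to discriminate.

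Aim 2 is meant to guide where these interventions are offered. Spurious provider-level predictors would misdirect that choice.

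**Working it through.** **Inputs.** From section 9.2: 191 providers, 1468 patients, ICC 0.07, 7 patients per provider, 30% against 41% prescribing, 80% power, type I error 5% (two-sided assumed). The stated totals give 1468/191 = 7.69 patients per provider, so both 7 and 7.69 are carried. Assumed, because the documents do not give it: the coefficient of variation (CV) of panel size.

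**1. The plan's own figure.** Two proportions, 0.30 against 0.41, need 314 patients per arm with continuity correction. The design effect is 1 + (7 − 1) × 0.07 = 1.42. Then 314 × 1.42 × 3 = 1337.6 patients, and 1337.6/7 = 191.1 providers. The stated 191 reproduces, so the plan's sample size already carries the inflation that section 9.1.2 leaves out. No sample size, power or error rate is stated for Aim 2.

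**2. Standard errors for a provider characteristic.** With equal panels, DE = 1 + (m − 1) × 0.07. The ordinary standard error is too small by √DE, and the true size of a nominal 5% test is 2 × [1 − Φ(1.96/√DE)]. With unequal panels, DE = 1 + [(1 + CV²)m − 1] × 0.07.

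| m | CV | DE | √DE | True size |
|---|---|---|---|---|
| 7 | 0 | 1.42 | 1.19 | 10.0% |
| 7.69 | 0 | 1.47 | 1.21 | 10.6% |
| 7.69 | 0.4 (assumed) | 1.55 | 1.25 | 11.6% |
| 7.69 | 0.6 (assumed) | 1.66 | 1.29 | 12.8% |
| 7.69 | 0.8 (assumed) | 1.81 | 1.35 | 14.5% |

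With equal panels, ordinary intervals are 1/1.19 = 0.84 to 1/1.21 = 0.83 of the correct width.

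**3. Check by simulation.** Beta-binomial outcomes with mean 0.41 and ICC 0.07, a null binary provider characteristic, 10,000 runs per setting, and 64 or 127 PCPs (one or two arms, since 191/3 ≈ 64). Ordinary logistic tests rejected in 10.8-10.9% of runs with equal panels and 12.9-13.2% at CV 0.6. PCP-clustered standard errors gave 5.1-6.4% across all settings, including CV 0.8.

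**4. Patient characteristics.** The relevant design effect is 1 + (m − 1) × 0.07 × (ICC of the characteristic itself). At m = 7.69, a characteristic with ICC 0 gives a size of 5.0%, and one with ICC 0.07 gives 5.4%. The problem is confined to variables that are constant, or nearly so, within a PCP.

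**5. Cross-validated C-statistic.** Illustration with 64 PCPs, ICC 0.07, pure-noise provider predictors, logistic regression, 10 folds and 400 runs:

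| Noise predictors | Folds by patient | Folds by PCP |
|---|---|---|
| 5 | 0.520 | 0.501 |
| 10 | 0.529 | 0.500 |
| 20 | 0.542 | 0.500 |

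A separate check with 5 and 10 predictors gave 0.518 and 0.533 by patient, against 0.495 and 0.503 by PCP. The effect on boosted models, trees and the net reclassification index was not computed.

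**The case against.** The strongest reply is that section 9.1.2 describes a prediction exercise. It states no hypothesis test, p-value, confidence interval or alpha. The only 5% error rate is in section 9.2, for each intervention arm against control. A reader might infer that Aim 2 has a 5% error rate which is really 10-14%. The documents do not support that, for two reasons. No such rate is set for Aim 2, so the inflation is conditional on coefficients being tested or given intervals. And the plan's inputs yield only about 10%; by the formula, about 14% needs an assumed panel-size CV of roughly 0.7-0.8. The condition is not far-fetched, because the goal in sections 2 and 6.2.2 is worded as association.

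Three further limits stand. The ICC of 0.07 belongs to Aim 1 prescribing. Responsiveness is not defined in section 9.1.2, so its ICC is unknown, and informative provider covariates would lower the residual value. That the logistic model is an ordinary one is inferred from silence. And the documents do not say that provider characteristics matter more to diffusion of responsibility than the others.

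It is also true that clustered standard errors leave the fitted probabilities unchanged, and with them the C-statistics and the reclassification index. They do nothing for boosted regression or trees. This widens the remedy and does not remove the point: the outputs that are named depend on how folds are formed, and the section is silent on that too.

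**Conclusion.** The point holds in conditional form. Section 9.1.2 should say how PCP clustering is handled, and at present it does not. If provider characteristics are tested or given intervals from ordinary logistic regression, standard errors are too small by about 1.2 and a nominal 5% test runs at about 10%. That rests on carrying the Aim 1 ICC over to Aim 2. Any higher figure, such as about 13% at a CV of 0.6, also rests on an assumed spread of panel sizes. If only C-statistics are reported, folds formed by patient would credit a handful of noise provider predictors with a C of roughly 0.52-0.53, on an illustrative simulation.

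A reader might extend this to all Aim 2 predictors or to the trial's main result. Neither follows: patient-level characteristics are barely affected, and Aim 1 is planned with GEE. This is a cheap improvement to one of the two aims.

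**What to change.** Add two sentences to section 9.1.2:

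- Cross-validation folds are formed by PCP, so that all patients of one PCP fall in the same fold, for the logistic, boosted and tree models alike.
- Any confidence interval or p-value for a characteristic comes from logistic GEE, or from logistic regression with standard errors clustered on PCP.

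Both are needed, since the first corrects the prediction measures and the second the inference. With about 64 PCPs per arm, ten folds hold about six PCPs each (64/10 = 6.4), so folds by PCP are workable.

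The cost is provider-level intervals about 20% wider at the plan's inputs (√1.42 = 1.19 to √1.47 = 1.21) and slightly lower C-statistics. No new data, software or design change is needed, and Aim 1 is untouched.
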